Effect of Professional Prophylaxis on Clinical Parameters and Patient Comfort:

Randomized Clinical Trial

12/01/2022

Study Protocol:

After the initial evaluation of the participants and their inclusion in the study, the participants were randomized in blocks into group A where a conventional protocol was used in quadrants I and III and the test protocol in quadrants II and IV, and group B where a conventional protocol was used in quadrants II and IV and the test protocol in quadrants I and III and III.

The observations were made at three different times: baseline, one week after the intervention, and three weeks after the intervention. (Figure 1)

The clinical assessment of each participant was performed using the the Ainamo & Bay gingival bleeding index (GBI), the O'Leary plaque control record (PCR) and the Silness and Löe plaque index (PI). (26–28) The primary outcome variable of the study was the Gingival Bleeding Index (GBI) with the Plaque Index (PI) as a secondary outcome variable.

Hard and soft deposits were removed according to the protocol assigned in one appointment performed by the principal investigator the day after the first data collection. The control protocol consisted of mechanical scaling with Woodpecker® scaler (Guilin, Guangxi, 541004 P.R.China) at power 1, followed by stain removal and polishing with R&S RUBBER DOME (R&S® Dental products [name]) with Prophy Paste CCS® polishing paste RDA 250 (Directa AB [name]) at a speed of 10,000 rotations per minute.

The test protocol consisted in an assessment of the periodontal status following the application of the plaque discloser (Biofilm Discloser, [name] & Co KG 64673 Zwingenberg - Germany), followed by oral hygiene instructions and biofilm removal with an erythritol jet (Airflow Plus Powder®, Electro Medical Systems S.A.), [name]) with the Airflow Prophylaxis Master® device (Electro Medical Systems S.A., [name]). The jet stream was used at a power of 3 and the irrigation at a power of 10. Calculus removal was then performed with the piezon scaller of the same device using a PS scaler tip (Electro Medical Systems® S.A., [name]).

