The first follow-up assessment (T1) was performed one week after the intervention, and the second follow-up assessment (T2) was performed 3 weeks after the intervention performed by the same research assistant that performed the initial assessment (T0). indeces The precision and accuracy of the data collection was ensured by calibrating the instruments used and the investigators to minimize and control possible measurement errors. The assistant investigator underwent calibration before the start of the study to train the indeces, followed by a discussion of the criteria with the principal investigator.

After the appointment the participant rated comfort using a Visual Analog Scale measured on a Likert scale of 0 to 10 for each quadrant.

Statistical Analysis Plan:

The sample size was calculated for a power of 80% to allow the study to detect a difference at the 0.05 significance level when the true difference between treatments is 0.5 units.

Data were entered into SPSS® software (Statistical Package for the Social Sciences, IBM, Armonk, NY, USA), version 27.

Descriptive and inferential statistics were performed to evaluate the results of the two protocols, with a significance level of 5%. The mean values and standard deviations of the clinical parameters were calculated per protocol and per study group, and for the 3

evaluation moments: for the initial moment (T0), for the evaluation at 1 week (T1), and for the final evaluation (T2).

Comparisons between evaluation moments in each protocol were evaluated using the nonparametric Wilcoxon test for paired samples.

The Mann-Whitney U test was used to analyze differences between protocols. The Friedman test was used to analyze the differences between the different evaluation periods.

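### The protocols are compared with an independent-samples test (Mann-Whitney U), although every participant receives both of them

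*Combined protocol and SAP*

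**What the plan says.** The Study Protocol section describes two randomized groups that differ only in which quadrants receive which protocol. The first is "group A where a conventional protocol was used in quadrants I and III and the test protocol in quadrants II and IV"; the second has the mirror-image assignment. Both protocols are therefore applied in every mouth. Gingival bleeding is the primary outcome variable and the plaque index is secondary. Comfort is also recorded within the person: the participant "rated comfort using a Visual Analog Scale measured on a Likert scale of 0 to 10 for each quadrant".

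For the comparison of protocols, the Statistical Analysis Plan says only: "The Mann-Whitney U test was used to analyze differences between protocols". A paired test does appear in the plan, but for another purpose: "Comparisons between evaluation moments in each protocol were evaluated using the nonparametric Wilcoxon test for paired samples". The Friedman test is likewise used for time. No mixed model, GEE or other allowance for pairing is given for the protocol comparison, and the unit of analysis (participant or quadrant) is not named.

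**The concern.** Test and conventional values from one mouth share that person's home care, diet and gingival susceptibility, so they are matched. The Mann-Whitney U test computes its standard error as if they came from different people. It keeps between-person variation in the error term, although that variation cancels in a within-mouth contrast.

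The plan names no primary analysis or time point, so calling this the primary comparison is an inference. It is well supported: the trial is sized on the contrast between treatments, and no other test of that contrast is listed. At stake is the meaning of a null result. A finding of no difference in bleeding, plaque or comfort could come from the choice of test alone.

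**Working it through.** **The plan's own figure.** The plan claims 80% power at the 0.05 level for the case "when the true difference between treatments is 0.5 units". This cannot be reproduced, because N, SD, correlation and sidedness are not stated. Taking a two-sided test and an assumed SD of 1.0:

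- Two independent samples: n per protocol = 2 × ((1.96 + 0.842) × 1.0 / 0.5)² = 62.8, so 63.
- Paired: participants = ((1.96 + 0.842) × 1.0 × √(2(1 − ρ)) / 0.5)², which is 63, 44, 32 and 19 for ρ = 0, 0.3, 0.5 and 0.7.

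Here ρ is the within-mouth correlation between the two protocol values. It is an assumption throughout.

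**Large-sample approximation, participant as unit.** The true variance of the mean difference is 2σ²(1 − ρ)/n. An unpaired test uses 2σ²/n, so its standard error is too wide by 1/√(1 − ρ). At nominal 5%:

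- type I error = P(|Z| > 1.96/√(1 − ρ))
- power, when paired power is 80% = P(Z > 1.96/√(1 − ρ) − 2.80)

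| ρ | SE too wide by | cut-off | type I error | power |
|---|---|---|---|---|
| 0 | 1.00 | 1.96 | 5.0% | 80% |
| 0.3 | 1.20 | 2.34 | 1.9% | 68% |
| 0.5 | 1.41 | 2.77 | 0.56% | 51% |
| 0.7 | 1.83 | 3.58 | 0.03% | 22% |

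**Simulation, trial sized for the paired comparison** (bivariate normal pairs, n = 34, effect set for 80% paired power). For ρ = 0.3, 0.5 and 0.7, Mann-Whitney type I error was 2.0%, 0.7% and 0.1%, and power was 62%, 47% and 21%. Signed-rank power was 75–77%. Repeat runs gave 2.0–2.4%, 0.7–1.1% and 0.1% for type I error, and 62–63%, 46–47% and 20–22% for power. With a bounded bleeding proportion (50 sites per protocol, ρ about 0.7, n = 34), type I error was 0.1% for Mann-Whitney and 5.5% for signed-rank; power was 15% and 65%.

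**Simulation, fixed difference of 0.5 and SD 1.0** (10,000 replicates; MW = Mann-Whitney, SR = signed-rank):

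| n | ρ | type I error, MW / SR | power, MW / SR |
|---|---|---|---|
| 32 | 0 | 4.6% / 4.9% | 48% / 47% |
| 32 | 0.3 | 2.3% / 5.1% | 47% / 61% |
| 32 | 0.5 | 0.8% / 5.1% | 47% / 77% |
| 32 | 0.7 | 0.1% / 4.9% | 48% / 93% |
| 63 | 0 | 5.0% / 4.7% | 77% / 77% |
| 63 | 0.3 | 2.0% / 4.9% | 81% / 90% |
| 63 | 0.5 | 0.7% / 4.9% | 85% / 97% |
| 63 | 0.7 | 0.1% / 5.2% | 91% / 99.9% |

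The tests agree at ρ = 0, as they should.

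**If quadrants are the rows.** Let the variances be P (participant), I (participant by protocol) and Q (quadrant). The true variance of the mean difference is (2I + Q)/n. The unpaired calculation on 2n rows per protocol uses (P + I + Q)/n. The test is therefore too liberal only if I exceeds P.

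- With I = 0 the ratio is Q/(P + Q), or 1 − ρ with ρ now the correlation between quadrants, so the test is conservative as before. Simulation at n = 32 gave 2.1%, 0.7% and 0.07% for 0.3, 0.5 and 0.7.
- With P = 0.1, I = 0.5 and Q = 0.4 the ratio is 1.4/1.0 = 1.4, and type I error = P(|Z| > 1.96/√1.4 = 1.66) = 9.8%.

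Across six assumed sets of variance components, simulated type I error ran from 0.5% to 10%.

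**The case against.** The strongest defence is that Mann-Whitney can be valid in this layout. Take a fixed within-participant contrast, such as quadrants I and III minus II and IV, and compare it between groups A and B. The plan does not say this. It says the test compares protocols, and it lists protocol and study group separately when it describes the summary statistics.

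Several points about size do stand:

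- The 21–62% power range assumes a trial sized by a paired calculation. If it was sized as two independent samples (63 participants at SD 1.0), Mann-Whitney power is 81–91% for ρ of 0.3 to 0.7. The test is then inefficient, but not short of the planned 80%.
- The error shrinks with ρ. At ρ = 0.1 the approximation gives a type I error of 3.9%, and at zero there is no error. A negative correlation reverses the direction: 7.9% at ρ = −0.3 with n = 32.
- With positive correlation the participant-level test is conservative, so a significant result would not be undermined.
- The quadrant-level inflation is hypothetical. The 9.8% example implies a correlation between protocol means of only 0.1/(0.1 + 0.5 + 0.2) = 0.125, below the 0.3 to 0.7 used elsewhere. Conservatism is the likelier outcome there too.
- The documents do not say why a split-mouth design was chosen, so no intention to gain power can be read into them.

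These points limit the size of the effect. They do not make the test fit the design.

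**Conclusion.** The concern holds, and the plan must be corrected on this point. The only test given for the protocol contrast assumes independence, which the design rules out; this follows from the text and needs no missing figure. What depends on assumptions is the size. For a within-mouth correlation of 0.3 to 0.7, the true type I error at participant level is about 2.0% down to 0.1% instead of 5%. In a trial sized for the paired comparison, power falls to about 62% down to 21%, against 75–77% for a paired rank test. The main risk is a false conclusion of no difference. If quadrants are entered as separate rows, the error can also go the other way, though only when participant-by-protocol variation exceeds between-person variation.

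**What to change.** Replace the Mann-Whitney sentence with wording such as:

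> For each index at each time point, and for comfort, one value per participant per protocol is formed over the two quadrants of that protocol (pooled sites for bleeding, mean for the other measures). Protocols are compared by the Wilcoxon signed-rank test on the within-participant difference, test minus conventional, with the Hodges-Lehmann estimate and 95% CI.

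Remove Mann-Whitney from all protocol comparisons. A mixed model with a participant effect, baseline and group A/B would be an acceptable alternative.

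Two statements should accompany the change: the time point at which bleeding is the primary comparison, and the N with the SD of within-participant differences on which the sample size rests.

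The cost is one replaced sentence plus these two statements. The signed-rank test is already in the plan for time comparisons, and the data and software stay the same. No participants or procedures are added. If the analysis has already been run, as the past tense of the plan may suggest, the protocol comparisons need to be rerun on the existing data.

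### The between-protocol test is unpaired and names no T0 adjustment, so this split-mouth comparison gives up precision

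*Combined protocol and SAP*

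**What the plan says.** Under Study Protocol, the design is split-mouth. One randomised group is described as "group A where a conventional protocol was used in quadrants I and III and the test protocol in quadrants II and IV", and the other group has the reverse assignment, so every participant contributes both protocols. The indices are GBI, PCR and PI: "The primary outcome variable of the study was the Gingival Bleeding Index (GBI) with the Plaque Index (PI) as a secondary outcome variable". On timing: "The observations were made at three different times: baseline, one week after the intervention, and three weeks after the intervention".

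Under Statistical Analysis Plan, three tests are named. Within a protocol: "Comparisons between evaluation moments in each protocol were evaluated using the nonparametric Wilcoxon test for paired samples". Across evaluation periods, the Friedman test. Between protocols: "The Mann-Whitney U test was used to analyze differences between protocols". T0 also appears in the descriptive means and SDs by protocol and by study group. For the between-protocol test the plan names no covariate, model or change score, no time point, and no choice between raw values and changes from T0.

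**The concern.** The question of the trial is whether the two protocols differ, and only the Mann-Whitney U test addresses it. That test treats the two sets of quadrants as independent samples, although both come from the same mouths, and it cannot take T0 into account as a covariate. Two sources of noise may therefore stay in the primary comparison:

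- variation between mouths, which pairing would remove;
- any lasting difference between a participant's two quadrant pairs, which pairing leaves in place and T0 could explain.

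At stake is the chance of detecting a real difference in GBI, and the width of any interval around it. The data needed to reduce both are already collected.

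**Working it through.** **The plan's own figure.** The sample-size statement gives 80% power to "detect a difference at the 0.05 significance level" "when the true difference between treatments is 0.5 units". No N, SD, sidedness, index or correlation is stated, so the 80% can be neither reproduced nor refuted. With two-sided testing assumed, n per protocol = 2 × (SD × (1.960 + 0.842) / 0.5)². This gives 16, 36, 63 and 142 for assumed SDs of 0.5, 0.75, 1.0 and 1.5.

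**Pairing and T0 compared.** A split-mouth trial was simulated with normal data, total SD 1, a true difference of 0.5, 32 participants and 3000 runs per scenario. All of these are assumptions. A share w of the variance belongs to the person, a share v to a side difference that persists from T0, and 1 − w − v is fresh at each visit. The within-mouth difference then has variance 2(1 − w), and its T0-to-follow-up correlation is r = v/(1 − w). Power:

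| w | v | r | Mann-Whitney, raw | Mann-Whitney, change | Unpaired ANCOVA on T0 | Paired Wilcoxon | Paired regression on T0 difference |
|---|---|---|---|---|---|---|---|
| 0.3 | 0 | 0 | 0.481 | 0.360 | 0.548 | 0.625 | 0.627 |
| 0.5 | 0 | 0 | 0.474 | 0.471 | 0.625 | 0.762 | 0.763 |
| 0.3 | 0.2 | 0.2/0.7 = 0.29 | 0.487 | 0.480 | 0.633 | 0.627 | 0.672 |
| 0.5 | 0.2 | 0.2/0.5 = 0.40 | 0.481 | 0.695 | 0.793 | 0.760 | 0.835 |
| 0.6 | 0.1 | 0.1/0.4 = 0.25 | 0.486 | 0.688 | 0.855 − 0.049 = 0.806 | 0.855 | 0.885 |

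- Pairing alone, against Mann-Whitney on raw values, adds between 14 points (0.487 to 0.627) and 37 points (0.486 to 0.855).
- After pairing, T0 adds almost nothing when the correlation is purely person-level (first two rows). It adds 3.0 to 7.5 points when side differences persist (last three rows). Part of any such step may reflect the move from a rank test to a linear model.
- In the two rows with v = 0.2, unpaired adjustment for T0 does at least as well as the paired Wilcoxon test (0.633 against 0.627; 0.793 against 0.760), because individual T0 values also carry the person effect. The two remedies overlap, so pairing is the likely larger loss and not a certain one. Using both is best or level in every row.
- With no true difference (2000 runs), Mann-Whitney on raw values rejected in 0.002 to 0.025 of runs, below the nominal 0.05. It is conservative here, not anti-conservative.

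**Size of the T0 step after pairing.** In large samples, adjustment multiplies the variance of the mean difference by 1 − r². From a paired test at 80% power, power = Φ(2.802/√(1 − r²) − 1.96), which is 0.816, 0.836 and 0.899 at r = 0.2, 0.3 and 0.5. This ignores the cost of estimating the slope. Simulating the regression itself against a paired t-test set at exactly 80%, with assumed sizes from 12 to 34 participants, gives:

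| r | Large-sample formula | 12 participants | 34 participants |
|---|---|---|---|
| 0.2 | 82% | 77% | 80% |
| 0.3 | 84% | 79% | 82% |
| 0.5 | 90% | 86% | 89% |

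**Change scores.** With equal variances, a change score multiplies the variance of the within-mouth difference by 2(1 − r). Power is then Φ(2.802/√1.4 − 1.96) = 0.658 at r = 0.3, and it breaks even at 0.800 when r = 0.5.

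**The case against.** The strongest case on the other side has four parts.

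First, the plan is silent on which values the Mann-Whitney test uses. They may be changes from T0, and T0 is also reported descriptively, so a T0 imbalance would be visible. This stands: it cannot be said that T0 is kept out of the between-protocol comparison. It does not remove the point, because a change score is not regression adjustment and the comparison would still be unpaired.

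Second, nothing in the documents supports a high r. Each protocol is averaged over two quadrants. If the usual quadrant numbering applies, I with III and II with IV are diagonal pairs, so a left-right habit largely cancels. Deposits are also removed in all quadrants between T0 and follow-up. This stands too, and it is why the T0 gain is conditional.

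Third, with few participants and low r the regression may gain nothing or lose slightly. The 12-participant column shows this.

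Fourth, a reader might infer that a chance T0 imbalance biases the reported protocol effect. The documents do not support that. Quadrant pairs are assigned by randomisation, so such an imbalance is ordinary sampling error that a valid test already allows for.

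**Conclusion.** The point holds as one of efficiency. For its central comparison the plan names only an unpaired test with no T0 adjustment, in a design where both protocols share a mouth and T0 is measured. The direction is firm for pairing whenever the two sets of quadrants in a mouth are positively correlated. For T0 it depends on r: about 86-89% power at r=0.5, but 77-80% at r=0.2, against 80% for an assumed paired t-test with 12 to 34 participants.

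A reader might infer a gain of 10 points or more from T0 alone. That would need r of at least 0.5 and the large-sample formula, starting from a paired test that the plan does not contain. A reader might also infer that the planned result would be invalid. Omitting T0 does not make it so, and ignoring positive within-mouth correlation makes the test conservative. All SDs, sample sizes and correlations used here are assumptions.

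**What to change.** - For each participant, compute the test-minus-conventional difference in GBI at T0, T1 and T2.
- Name T1 or T2 as the primary time point.
- Regress the follow-up difference at that visit on the T0 difference. Do not centre the T0 difference at its sample mean, since the intercept would then be the unadjusted mean difference.
- Report the intercept, which is the protocol effect at zero T0 difference, with its 95% CI and p-value as the primary between-protocol result.
- Repeat for the other visit and for PI and PCR.
- Pre-specify a rank-based sensitivity analysis, to be run whatever the residuals look like.

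The model works on within-participant differences, so it supplies the pairing and the T0 adjustment together. Adding T0 to an unpaired comparison would leave the pairing out.

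The cost is revised SAP wording, one linear model per index and visit in SPSS, and one degree of freedom in each. There is no gain, or a slight loss, if r is low and participants are few. No new data, visits or participants are needed. The plan is written in the past tense; if outcome data have already been analysed, the change should be reported as made after the fact.
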